1.1.4. Main Treatment Options

The WHO-recommended treatment strategy for DS-TB is directly observed treatment short-course (DOTS). DOTS combines 5 elements: political commitment; microscopy services; drug supplies; surveillance and monitoring systems; and use of highly efficacious regimens with direct observation of treatment. The standard WHO chemotherapy treatment regimen for DS-TB consists of a 2-month intensive phase during which 4 drugs are administered once or twice per week (isoniazid, rifampicin, pyrazinamide, and ethambutol), with a continuation phase of 4 months during which 2 drugs are administered (usually isoniazid and rifampicin) to which the mycobacterium has been demonstrated to be sensitive for 4 months (Chan 2002⁶, Douglas 1999⁸). Streptomycin is also used as a first line drug to treat DS-TB, usually for retreatment of newly diagnosed cases that failed to complete the initial treatment course or are responding poorly to their first course of TB treatment.

MDR-TB is considered curable but cannot be adequately treated with the standard short-course therapy (SSCT) (Chan 2002⁶, Douglas 1999⁸). MDR-TB therapy often requires extensive chemotherapy (up to 2 years of treatment) with a combination of less efficacious second line drugs, requires extensive supervision and treatment costs are extremely expensive. Most authorities recommend a regimen consisting of either 3 or 4 oral anti-TB drugs in combination with 1 injectable drug (Frieden 1999¹²).

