1.1.5. Mortality and Morbidity

MDR-TB represents a major threat to global TB control. On average, these patients require a treatment duration of 2 years on average with the substantially more toxic and less potent second-line anti-TB drugs. Cure rates are lower and mortality higher than for DS TB, particularly if patients are coinfecting with HIV. According to the latest WHO data, only 48% of the MDR-TB patients in the 2010 cohort of detected cases were successfully treated, reflecting high mortality rates and loss to follow-up (WHO 2013²⁷).

Mortality and case fatality estimates are uncertain partly due to incomplete coverage of global drug resistance surveillance and the lack of direct measurements of MDR-TB deaths. An estimated 170,000 (range 102,000 to 242,000) deaths caused by MDR-TB occurred in 2012, including those with HIV infection (WHO 2013²⁷). This high overall mortality reflects poor diagnostic and treatment capacity for MDR-TB globally. Even for patients that make it into good treatment programmes, overall mortality still exceeds 10%, with a range of 8% to 21% (Wells 2010²⁴). Two independently conducted meta-analyses from 2009, each including approximately 30 studies in MDR-TB, found death as a reported outcome in 11% of treated patients (Johnston 2009¹⁷, Orenstein 2009²²). A more recent meta-analysis reflecting data from 9,153 individual patients reported a mortality rate of 15% (95% CI: 14.5% to 16%). Patients who died were significantly older, more likely to be HIV co-infected, with more extensive disease (defined as acid fast bacilli [AFB]-smear positive or cavities on chest x-ray if no information about AFB-smear), and/or had prior therapy (Ahuja 2012¹).

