2. OVERVIEW OF STUDY DESIGN

2.1. Study Design

The research design uses a prospective observational comparative cohort study of patients treated for MDR-TB in multiple countries included in the early adopter (WHO pilot) program. A case of tuberculosis is one in which a health worker (clinician or other medical practitioner) has diagnosed TB. MDR-TB is defined as TB caused by *Mycobacterium tuberculosis* resistant in vitro to the effects of isoniazid and rifampicin, with or without resistance to any other drugs. Patients are enrolled in the registry by their healthcare provider once the healthcare provider diagnoses a patient with MDR-TB (inception cohort for comparison) or decides to treat with BDQ (exposure cohort specifically identifying indication for use for BDQ). All patient follow-up data will be collected at each visit from the healthcare provider during the course of BDQ treatment and for an additional 24 months after the last BDQ dose unless the patient is lost to follow-up or has died. Similar follow-up will be conducted for MDR-TB patients not treated with BDQ. Two options are under evaluation for the recruitment of MDR-TB patients not treated with BDQ. The first option under consideration is to include patients who are eligible for BDQ, but refuse BDQ at sites where BDQ is available. The second

option under consideration is the use of a stepwise cluster wedge design to enroll patients at centers who would be eligible for BDQ, but do not have access. The method for selecting MDR-TB patients not treated with BDQ will depend on how BDQ is made available in the early adopter countries. All patients newly diagnosed and treated for MDR-TB will be eligible for inclusion in the registry. Additionally, all patients initiating BDQ treatment will be eligible for inclusion in the registry regardless of the indication for use. All patients meeting the inclusion criteria and providing informed consent for participation in the study will be enrolled. The registry enrollment period will be open for 36 months with an additional 24 months of follow-up for safety assessment. This enrollment period should allow the enrollment of approximately 3000 MDR-TB patients treated with BDQ.

Data will be collected in an observational manner such that the management of the patient is determined by the patient and the caregiver and not influenced by the registry protocol. The registry will describe care as it is provided.

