4.2.2. Outcome Definitions and Measures

The registry is designed to observe several aspects of MDR-TB treatment such as drug utilization characteristics, treatment outcomes (clinical and microbiologic), and safety outcomes (adverse events and mortality). All study outcomes will be documented by the healthcare provider and will be reported up to 24 months after discontinuation of MDR-TB treatment.

Study outcome definitions will include:

- Medical indication for BDQ treatment as reported by the healthcare provider
- Frequency of use of expert medical consultation in MDR-TB treatment with BDQ
- Drug susceptibility of MDR-TB isolates (Pre-XDR, XDR) and drug susceptibility to BDQ based on MIC reported

-
- Laboratory location and type performing susceptibility testing as well as type of test performed
 - Past treatment history, past medical history, prior medications utilization, and health care site of treatment
 - Use of DOT for drug administration
 - Adverse events including deaths over the course of MDR-TB therapy recorded using WHO guidance for pharmacovigilance of medicines used in the treatment of tuberculosis (WHO 2012²⁵)
 - Comorbidities prior to initiating MDR-TB therapy as well as over the course of therapy
 - Concomitant medications prior to initiating MDR-TB therapy as well as over the course of therapy
 - Reason for discontinuation of MDR-TB therapy
 - Change in TB background regimen (Y/N)
 - Cavities on chest x-ray
 - Acid fast bacilli-smear $\geq 1+$ (Y/N)

The following definitions will be used for treatment outcomes among MDR-TB cases (WHO, 2013³⁰):

- Cured: Treatment completed as recommended by the national policy without evidence of failure AND three or more consecutive cultures taken at least 30 days apart are negative after the intensive phase^a.
- Treatment Completed: Treatment completed as recommended by the national policy without evidence of failure BUT no record that three or more consecutive cultures taken at least 30 days apart are negative after the intensive phase^a.
- Treatment Failed: Treatment terminated or need for permanent regimen change of at least two anti-TB drugs because of:
 - Lack of conversion^b by the end of the intensive phase^a, *or*
 - Bacteriological reversion^b in the continuation phase after conversion^b to negative, *or*

-
- Evidence of additional acquired resistance to fluoroquinolones or second-line injectable drugs, *or*
 - Adverse drug reactions (ADRs).

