4.2.4. Length of Follow-up

Each patient will be followed for 24 months from the discontinuation of MDR-TB therapy, until death, or loss to follow-up within the cohort, whichever occurs first. Time varying variables will be recorded at each patient visit.

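### A registry that closes 24 months after enrollment ends cannot give late enrollees the 24 months after MDR-TB therapy that Section 4.2.4 promises each patient

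*Protocol*

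**What the plan says.** The synopsis and Section 2.1 give the calendar: "The registry enrollment period will be open for 36 months with an additional 24 months of follow-up for safety assessment".

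Section 4.2.4 gives the rule for the individual patient: "Each patient will be followed for 24 months from the discontinuation of MDR-TB therapy, until death, or loss to follow-up within the cohort", whichever comes first. It lists no administrative close. Section 4.2.2 uses the same anchor: study outcomes "will be reported up to 24 months after discontinuation of MDR-TB treatment".

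The synopsis and Section 2.1 also carry a second anchor. Follow-up data are collected "during the course of BDQ treatment and for an additional 24 months after the last BDQ dose", and "Similar follow-up will be conducted for MDR-TB patients not treated with BDQ", although those patients have no BDQ dose to count from.

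Patients enter at diagnosis of MDR-TB or at the decision to give BDQ (Section 2.1), so most of their treatment lies after entry. On its length, Section 1.1.4 speaks of up to 2 years, and Section 1.1.5 says that "these patients require a treatment duration of 2 years on average".

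Section 7.3.1 completes the study three years after registry start, which is when enrollment closes under Section 2.1.

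**The concern.** The time left after enrollment closes equals the post-treatment period alone. It leaves no room for the treatment that comes first. A patient enrolled in month 36 and treated for 24 months would stop therapy at about month 60 and finish follow-up at about month 84.

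Late deaths and late adverse events are at stake. They would be seen mainly in early enrollees, and a report that patients were followed for 24 months after treatment would be untrue for many of them. The comparison of event and mortality rates between BDQ-treated and other patients is a primary objective (Section 1.3.1), so it also matters whether the two cohorts are cut off to the same degree. Changing the three-year completion date in Section 7.3.1 to 60 months would not remove the problem.

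**Working it through.** **Inputs.** Enrollment runs over months 0 to 36 and is followed by 24 months (Section 2.1). Each patient is due 24 months after therapy (Sections 4.2.2 and 4.2.4). T is the time on treatment after entry: 24 months from the average in Section 1.1.5, with 18 and 12 as a range. Uniform accrual is an assumption, because the protocol does not state the accrual pattern.

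**The plan's calendar.** 36 + 24 = 60 months. To give every patient the full period, the registry needs 36 + T + 24 months. That equals 60 only if T = 0. For T = 24 it is 84, and for T = 18 it is 78.

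**Section 4.2.4 anchor, close at month 60.** A patient enrolled at month e has 60 − e − T months after treatment, bounded between 0 and 24. The full 24 months needs e ≤ 36 − T. The share completing is therefore (36 − T)/36, and the share falling short is T/36.

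| T (months) | Complete | Fall short | Mean post-treatment months | Enrolled at month 36 |
|---|---|---|---|---|
| 24 | 12/36 = 33% | 67% | (12×24 + 24×12)/36 = 16 | 0 |
| 18 | 18/36 = 50% | 50% | (18×24 + 18×15)/36 = 19.5 | 6 |
| 12 | 24/36 = 67% | 33% | (24×24 + 12×18)/36 = 22 | 12 |

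**Accrual shape, T = 24.** If accrual rises linearly from zero, (12/36)² = 11% complete and 89% fall short. If it declines linearly to zero, 1 − (24/36)² = 56% complete and 44% fall short.

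**Deaths.** These shares describe patients still under observation, since death ends follow-up legitimately. With the 15% mortality quoted in Section 1.1.5, the share of all enrolled is 0.67 × 0.85 = 57%. Losses to follow-up lower it further.

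**Last-BDQ-dose anchor.** The length of the BDQ course is not in the document. Assuming 3 to 12 months from entry, 3/36 = 8% to 12/36 = 33% of BDQ patients fall short, and the last enrollee still has 21 to 12 months.

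**Unequal cut-off (illustration).** Suppose comparators enroll in months 0 to 18 and BDQ patients in months 18 to 36, as could happen if centers move from no access to access. With T = 24 and the 4.2.4 anchor:
- Comparators average (12×24 + 6×21)/18 = 23 post-treatment months, and 12/18 = 67% complete.
- BDQ patients range from 18 down to 0 months, average 9, and none complete.

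**The case against.** **The month-60 close is an inference.** No section names month 60 or a data cut-off, and the additional 24 months could be read as a per-patient period. That would remove the contradiction with 4.2.4 but leave the registry without an end, except for the three years in Section 7.3.1. A close at month 36 is worse: with T = 24 nobody could reach 24 post-treatment months, and the 67% enrolled after month 12 would have none. The calendar reading is the more natural and the more favourable one, but it remains a reading.

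**A reader might infer that most patients miss the promised follow-up and that the last get none, whatever the circumstances.** The document does not support that:
- Under uniform accrual, a majority falls short only if treatment after entry exceeds 18 months.
- None at all requires entry near month 36 and a full 24 months of treatment.
- The 2-year figures come from background text, and one of them is an upper limit.
- BDQ patients may enter after background therapy has begun, which shortens T.
- On the last-BDQ-dose anchor, with the assumed courses, neither statement holds for BDQ patients.

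**Much of the analysis is protected.** Section 4.4.2.2 uses person-time rates and Poisson regression, which allow for unequal observation. Treatment-emergent events end 30 days after the last BDQ dose (Section 4.2.2.1), and the WHO outcomes for MDR-TB cases concern the treatment period. Even the month-36 enrollee treated for 24 months finishes by month 60. This stands, with one limit: person-time removes the effect of unequal follow-up only if event rates are the same during and after treatment.

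**Bias between cohorts is not established.** A reader might infer that BDQ patients will be cut off more often. That is plausible under the stepped-wedge option in Section 2.1. It does not follow under the other option, in which patients who refuse BDQ enroll alongside those who accept it. The protocol leaves the choice open.

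**Conclusion.** The inconsistency holds. With a close at month 60, the registry cannot give every patient 24 months after MDR-TB therapy for any treatment length above zero. At the protocol's 2-year average and uniform accrual, about 67% of patients still under observation fall short, and late enrollees have almost no post-treatment time. The figure is 50% at 18 months and 33% at 12. On the last-BDQ-dose anchor it is about 8% to 33% of BDQ patients for assumed courses of 3 to 12 months, so smaller but not zero.

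The damage is confined to post-treatment deaths and late adverse events. It becomes unequal between cohorts if comparators enroll earlier than BDQ patients. This is a should-fix: the stated follow-up is a property that the design does not have, but the on-treatment results largely stand.

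**What to change.** Reconcile the synopsis and Sections 2.1, 4.2.2, 4.2.4 and 7.3.1:

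- Choose one follow-up anchor that can be applied to both cohorts, and one closing date for the registry.
- Add the administrative close to Section 4.2.4 as an end of follow-up, beside death and loss.
- State that the full 24 months applies only to patients whose anchor date falls at least 24 months before the close, which is month 36 for a close at month 60.
- Censor at the close. Report post-treatment deaths and adverse events on observed person-time, with the numbers still under observation, by cohort.

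This costs protocol wording and a less favourable statement of follow-up. The alternative is to keep the promise in 4.2.4 and run the registry until 24 months after the last patient stops therapy, about month 84 with 2 years of treatment. That costs up to 24 more months of operation and is optional.

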2.2. Study Design Rationale

The prospective observational comparative cohort design of the registry was chosen to specifically meet the study objectives. Prospective data collection not only facilitates characterization of clinics treating MDR-TB patients and how care is delivered, as well as patients being treated, but also facilitates active pharmacovigilance via real-time identification and reporting of adverse events, including deaths. By including MDR-TB patients as well as all patients treated with BDQ, the study is able to assess the indication for BDQ use, as well as how BDQ is used. By including patients treated with BDQ and MDR-TB patients not treated with BDQ, the study is able to provide an assessment of the relative risk of adverse events and deaths for BDQ relative to the observed risk among similar MDR-TB patients. The study design also provides for drug sensitivity testing over time for MDR-TB patients as well as the possibility of collecting samples for future drug sensitivity testing. The registry design was chosen due to the limited data on BDQ utilization and treatment outcomes (clinical and microbiologic) as well as the limited information on treatment outcomes for other MDR-TB treatments. Patients will be treated at a limited number of healthcare sites under the early adopter program (WHO pilot sites) which facilitates targeting healthcare providers who treat MDR-TB with educational material on the importance of enrolling patients in the registry.

3. STUDY POPULATION

3.1. Patient Selection

3.1.1. Inclusion Criteria

The study population will be drawn from the population of all patients treated for MDR-TB in multiple countries. All patients newly diagnosed with MDR-TB as well as all patients newly treated with BDQ at participating sites will be eligible for inclusion in the registry. All patients meeting registry inclusion criteria will be eligible for inclusion in the registry provided they submit the necessary informed consent for participation.

3.1.2. Exclusion Criteria

No specific exclusion criteria will be applied in this study other than those scenarios that follow from the inclusion criteria.

3.1.3. Data Source(s)

3.1.3.1. Healthcare Providers

Data for the registry will be gathered by healthcare providers treating patients MDR-TB at participating centers that evaluate, diagnose and treat patients with MDR-TB. Data will be recorded at patient enrollment and at each subsequent patient visit.

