Additionally, the World Health Organization (WHO) issued interim policy guidance on the use of BDQ in the treatment of MDR-TB and specified the essential treatment and management conditions for the use of BDQ. The interim policy guidance identified the need for collection of additional data to further evaluate the benefits and risks of BDQ treatment beyond data provided from the BDQ Phase II clinical development program. Specifically, the interim guidance identified the need to collect additional data from larger patient populations representative of the target population for BDQ treatment that would be able to yield results with high precision and generalizability to global populations with respect to efficacy, safety, and emergence of resistance to BDQ or to drugs in background regimen.

Janssen Research and Development LLC proposes the establishment of a prospective, multi-country MDR-TB registry to further assess the benefits and risks of BDQ by evaluating BDQ safety, effectiveness, and emergence of resistance, BDQ drug utilization, and adherence to WHO guidance in the use of BDQ in MDR-TB treatment. The following primary objectives were specifically chosen to address gaps in the currently available data informing BDQ benefits and risks:

- To describe the type of hospital or outpatient setting administering MDR-TB treatment
- To describe MDR-TB treatment delivery modalities, including treatment and management programs in place, administration of drug under closely monitored conditions, and consultation with experts in clinical management of MDR-TB and public health authorities such as national MDR-TB advisory groups within National TB Control Programs
- To describe the demographic and clinical characteristics of MDR-TB patients participating in the registry
- To describe MDR-TB treatment regimen utilization including dosages, duration, past treatment history, past medical history, concomitant medications used for conditions other than TB
- To measure adherence to WHO guidance in terms of selection of MDR-TB regimens and selection of patients for BDQ treatment
- To describe the indication for use of BDQ
- To measure extent to which patient informed consent is obtained for receipt of BDQ
- To describe BDQ and background drug susceptibility testing expressed as minimum inhibitory concentration (MIC) at baseline and for isolates from the last positive specimens

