4. STATISTICAL METHODS

4.1. Sample Size and Study Precision

The three year enrollment period of the registry is estimated to result in an enrollment of 3000 to 5000 BDQ-treated patients.

A cohort of 3000 patients gives a 95% probability of identifying an adverse event with an incidence rate of 1:1000.

Based on the sample size estimates below, a registry of 1000 BDQ-exposed patients would have 95% power to detect a Relative Risk of 2 assuming $\alpha = 0.05$ and a 1:1 ratio of BDQ-exposed patients to unexposed patients for events that occur with a frequency of at least 3%.

Power and Sample Size for Adverse Events Occurring with a Frequency of at Least 3%							
Exposed	Relative Risk						
	1.5	2	3	4	5	7	10
0	0.049985	0.049985	0.049985	0.049985	0.049985	0.049985	0.049985
100	0.133214	0.252768	0.559428	0.828643	0.961157	0.999754	1.000000
200	0.190756	0.414883	0.844041	0.986772	0.999721	1.000000	1.000000
300	0.243884	0.552078	0.952777	0.999299	0.999999	1.000000	1.000000
400	0.294233	0.663681	0.987120	0.999970	1.000000	1.000000	1.000000
500	0.342210	0.751574	0.996745	0.999999	1.000000	1.000000	1.000000
600	0.387925	0.819043	0.999224	1.000000	1.000000	1.000000	1.000000
700	0.431400	0.869774	0.999824	1.000000	1.000000	1.000000	1.000000
800	0.472639	0.907271	0.999961	1.000000	1.000000	1.000000	1.000000
900	0.511649	0.934588	0.999992	1.000000	1.000000	1.000000	1.000000
1,000	0.548449	0.954244	0.999998	1.000000	1.000000	1.000000	1.000000

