4.3.2. Specific Comparisons

The observed rates of adverse events and death among BDQ-treated patients will be compared with the observed rates of adverse events and death among patients with similar clinical characteristics, but not treated with BDQ.

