4.4.2.2. Analysis of Adverse Events

Incidence rates of adverse events will be calculated for the BDQ and non-BDQ treated cohorts. Additional descriptive analyses will include incidence rates of adverse events of interest for BDQ treated patients and non-BDQ treated patients calculated by dividing the total number of each adverse event by the total person-exposure time and expressed as the number of events per person-year, and 95% confidence intervals.

Relative risk rates and 95% confidence intervals will be calculated and appropriate stratified analyses will be conducted for each adverse event, including death. Poisson regression models will be used to adjust for potential confounders based on baseline clinical characteristics and patient demographics. Adjustments for imbalances between the treatment groups will be applied using accepted methods based on sample size availability and the observed overlap of key patient characteristics. If the sample size is adequate, propensity score methods may be used to adjust for imbalances between the 2 treatment groups before receiving the BDQ treatment or other MDR-TB therapy. Adjustment methods will be determined *a priori* to any comparative analysis with respect to safety outcomes.

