7. ADMINISTRATIVE REQUIREMENTS

7.1. Adverse Event Reporting

This study is based on aggregate analyses, and the sponsor will report aggregate findings as study reports. Due to the prospective design of this study, in instances where an HCP identifies adverse events or serious adverse events, regardless of causality, the events will be captured by staff at the RCC during the registry data collection process, and an AE form will be forwarded to the Sponsor for review and to be entered to the Sponsor's Safety database. The events will be reported as individual case safety reports under timelines as appropriate per company standard operating procedures.

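### Adverse events are documented at routine-care visits the registry does not schedule, and the planned baseline or propensity adjustment cannot remove any difference in detection between BDQ and comparator patients

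*Protocol*

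**What the plan says.** **How events are found.** Section 4.2.2 has the healthcare provider document every study outcome. Section 3.1.3.1 states when: "Data will be recorded at patient enrollment and at each subsequent patient visit". Section 7.1 states what triggers a report: "in instances where an HCP identifies adverse events or serious adverse events, regardless of causality, the events will be captured by staff at the RCC". Section 2.1 leaves patient management to patient and caregiver, free of influence from the registry.

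**What is promised about equal follow-up.** The objectives in 1.3.1 include active monitoring of adverse events by cohort event monitoring. Section 2.1 promises similar follow-up for patients not treated with BDQ. Neither statement is accompanied by an assessment schedule.

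**What is compared.** A relative risk of adverse events and death, BDQ against no BDQ, is a primary objective. Section 4.3.2 states: "The observed rates of adverse events and death among BDQ-treated patients will be compared with the observed rates" in clinically similar patients not given BDQ. Section 4.4.2.2 divides event counts by person-exposure time and plans relative risks for each adverse event, death included.

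**What is adjusted.** Section 4.4.2.2: "Poisson regression models will be used to adjust for potential confounders based on baseline clinical characteristics and patient demographics". It also allows stratified analyses, and propensity scores for imbalances present before treatment. Section 4.5 makes the safety comparison conditional on propensity-score overlap of about 750 patients per group. Section 5 names channelling, loss to follow-up and uncollected data as limitations. It does not name detection bias.

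**The concern.** An adverse event rate built from provider records is the product of two things: how often events occur and how often they are noticed and recorded. Where both cohorts are examined equally often, the second factor cancels in the rate ratio. Nothing in the protocol ensures that here, because visits follow local care.

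The events most exposed are those found mainly by contact or testing. Section 4.2.3 lists risk factors for QT prolongation, electrolyte abnormality, arrhythmia and liver disease, so events of this kind are plainly of interest. All-cause death is much less exposed.

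A difference in visit or test frequency arises after baseline. Baseline covariates and a propensity score balance who enters each cohort; they do not balance how closely patients are watched afterwards. Two cohorts could overlap perfectly in propensity score, pass the check in 4.5, and still yield a relative risk away from 1 with no drug effect. The opposite can also happen: denser observation of the comparators would hide a real excess. Either error would matter in a post-marketing registry whose purpose is to inform benefit and risk.

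**Working it through.** **Inputs from Protocol 4.1.** 1000 BDQ-exposed patients, "and a 1:1 ratio of BDQ-exposed patients to unexposed patients", a comparator event frequency of 3%, alpha 0.05 with sidedness not stated, and an expected 3000 to 5000 BDQ-treated patients. From 4.5: about 750 per group as the minimum overlap.

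**Input not in the documents.** The capture ratio r, meaning the probability that an event is recorded in a BDQ patient divided by that probability in a comparator. It is assumed, over the range 1.1 to 2.0.

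**Step 1: reproduce the plan's figure.** The plan states that "a registry of 1000 BDQ-exposed patients would have 95% power to detect a Relative Risk of 2"; its table gives 0.954. For two proportions with n per group,

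power = Φ{ [ (p1 − p0) − z·√(2p̄(1−p̄)/n) ] / √( [p0(1−p0) + p1(1−p1)]/n ) }, where p̄ = (p0 + p1)/2.

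With p0 = 0.03, p1 = 0.06, n = 1000:
- one-sided 5% (z = 1.645): (0.030 − 1.645 × 0.00927)/0.00925 = 1.595, power 0.945;
- two-sided 5% (z = 1.960): 1.279, power 0.900.

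The one-sided result is close to the table. At RR 1.5 the one-sided value is 0.548 against the table's 0.548 (two-sided 0.423). The table is therefore consistent with a one-sided 5% test. That is a separate matter; both versions are shown below.

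**Step 2: apply the same formula with no drug effect.** If the true relative risk is 1, the observed relative risk equals r. Set the observed comparator frequency to p0 = 0.03 and the observed BDQ frequency to p1 = 0.03r. The formula then gives the chance of declaring a BDQ excess.

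Worked case, r = 1.5, n = 1000, two-sided: p1 = 0.045, p̄ = 0.0375; (0.015 − 1.960 × 0.00850)/0.00849 = −0.195; Φ = 0.423.

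| Assumed r | 750 per group, two-sided / one-sided | 1000 per group | 3000 per group |
|---|---|---|---|
| 1.1 | 5% / 10% | 6% / 10% | 10% / 16% |
| 1.2 | 10% / 16% | 11% / 19% | 25% / 37% |
| 1.5 | 33% / 45% | 42% / 55% | 86% / 92% |
| 2.0 | 80% / 88% | 90% / 94% | over 99% |

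With r = 1 the chance of a false excess is 2.5% (two-sided test) or 5% (one-sided). The 3000 column assumes as many comparators as BDQ patients, which the protocol does not promise.

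**Step 3: read the table.** A larger registry makes a false excess more likely, because the bias stays fixed while the standard error shrinks. The mechanism is symmetric: with r below 1, a true relative risk of 2 is observed as 2r, for example 2/1.5 = 1.33.

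**The case against.** **The direction is not documented, and a reader might infer that it is.** It is tempting to conclude that BDQ patients are monitored more closely and that the relative risk will therefore be inflated. The documents do not support that. The Synopsis says the WHO guidance "specified the essential treatment and management conditions for the use of BDQ"; it does not mention monitoring there. The reference to closely monitored conditions in 1.3.1 belongs to the objective on MDR-TB treatment delivery as a whole, so it covers both cohorts. No section says BDQ patients have more visits or tests. This objection stands, and the point is limited accordingly.

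**Some of the text points towards comparability.** Similar follow-up is promised. One of the two comparator options in 2.1 is patients who decline BDQ at sites that have it, so providers would be the same. The other involves centres without access, and the choice is open. Directly observed therapy could bring contact well beyond clinic visits. All this makes a large difference less certain. It does not show that detection is equal, because no procedure is attached to the promises.

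**The analysis is not confined to one adjusted model.** Section 4.4.2.2 also allows stratified analyses and other accepted methods, and a separate analysis plan, not available here, may add detail. However, the methods named in the protocol all address imbalance between the groups at baseline.

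**It is unclear whether post-treatment time enters the adverse event rate.** Section 4.2.2 lists adverse events over the course of therapy but also reports outcomes for 24 months after it. That is a reason to tabulate visits by period, not evidence that sparsely observed time dilutes the rate.

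**Conditioning on visit frequency can itself bias.** Visits are post-baseline and may increase because an event occurred. This stands, and it rules out restriction or stratification by visit frequency as the main analysis.

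**Conclusion.** The concern holds in a limited form. The protocol makes a relative risk for every adverse event a primary comparison, takes the events from unscheduled provider visits, and names only adjustments that act on baseline differences. It gives no means of seeing whether detection was equal and does not list unequal detection as a limitation.

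The size is conditional. At 1000 per group and a two-sided 5% test, a capture ratio of 1.2 raises the chance of a false BDQ excess from 2.5% to 11%, and a ratio of 1.5 raises it to 42%; at 3000 per group the figures are 25% and 86%. They rest on an assumed ratio, 3% observed in comparators, equal group sizes and no drug effect. They show how sensitive the comparison is and do not forecast its result. The protocol gives no visit or test frequency for either cohort, so a ratio of 1 is not excluded, nor is a ratio below 1 that would mask a real excess. Death is little affected.

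**What to change.** In 4.3.2 and 4.4.2.2, keep the planned relative risks and add:

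- **(a)** a table of visits per person-month by cohort and by period (on treatment, after treatment), with relevant tests where these are recorded;
- **(b)** a statement, made before any comparative analysis, that death and serious adverse events form the comparison least dependent on visit frequency, noting that hospitalisation may still vary with care setting;
- **(c)** a rule that, if visit or test rates differ materially between cohorts, relative risks for non-serious and laboratory- or ECG-detected events are reported as descriptive and not as evidence of a drug effect, with what counts as material fixed in advance;
- **(d)** in section 5, detection bias as a named limitation.

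Any stratification by visit frequency should be a sensitivity analysis only.

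**Cost.** Wording changes and a few tables, with no added visits or procedures. Section 3.1.3.1 has data recorded visit by visit, so visit counts should be obtainable; the protocol does not say whether test counts are collected. The real price is that fewer types of adverse event would carry a comparative claim if the cohorts turn out to be observed unequally.
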